2.1 OBJECTIVES AND SCIENTIFIC AIMS

Primary objective:

- To determine non-inferiority of ABPI when compared to BioSentry in reducing the rate of iatrogenic pneumothorax during the routine observation stay within 2 hours following image guided lung biopsy.

Secondary objective:

- To evaluate ABPI and BioSentry in reducing the rate of iatrogenic pneumothorax during the routine observation stay within 2 hours following image guided biopsy in a per-protocol analysis.
- To evaluate ABPI and BioSentry in reducing the rate of chest tube placement for pneumothorax up to two weeks following lung biopsy.
- To evaluate ABPI and BioSentry in reducing the rate of delayed pneumothorax up to two weeks following lung biopsy.

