An autologous blood patch consists of using the patient's coagulated blood to seal the puncture site at the end of a lung biopsy. The earliest report of its potential role in decreasing the incidence of pneumothorax was in 1988 where it was used in a limited number of patients, and though the results were not statistically significant, it did show a decrease in pneumothorax rate from 34.1% to 28% and a decrease in chest tube insertion rate from 9% to 7.7% [14]. Since then multiple other studies have evaluated the usefulness of the blood patch technique. Lang et al. showed a significant reduction in pneumothorax rate from 47% to 9% (p<0.05) in a study in 2000, and most recently in 2013, a randomized clinical trial was published in American Journal of Roentgenology (AJR) supporting the use of ABPI, mainly in reducing the rate of chest tube placement and admission from 18% to 9% (p<0.05) and similarly showing a trend in the reduction of pneumothorax rate from 35% to 26% (p>0.05)[15,16]. Following that same rationale, manufactured plugs have also been developed in recent years toward the same purpose. One such material is the BioSentry hydrogel plug developed by Angiotech and approved by FDA. BioSentry is deployed at the visceral pleural puncture site through the introducer needle using a deploying device (Figure 1). It swells upon contact with moisture and seals the pleural puncture site. It is absorbed by the patient's body over time. A supportive study of BioSentry by Zaetta et al. demonstrated a significant reduction of pneumothorax rate from 31% to 18%, and also a reduction –albeit non-significant- in the chest tube insertion rate from 11% to 4% compared to an untreated control group [13]. In an observation at our institution between 2007 and 2009, 181 consecutive patients undergoing lung biopsy by the author received blood patch. The rates of pneumothorax and chest tube placement, 6.6% (12/181) and 1.1% (2/181) respectively, were significantly lower than our group historical averages. Both of these techniques -either ABPI or BioSentry - along with "no plugging" are routinely used during lung biopsy procedures performed in our institution. Although both ABPI and BioSentry techniques have been independently validated in reducing the rate of pneumothorax and chest tube placement compared to controls, no head-to-head comparison has been made as to the effectiveness of these two techniques to justify the use of one over the other. There is no measurable added cost related to use of ABPI since the nursing personnel used in acquiring and handling the blood specimens are also involved in the patients' procedural sedation and thus perform these services within the scope of the procedure. Up to two standard stock syringes and

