4.3 Intervention

Patients with a focal lung lesion amenable to needle biopsy who meet initial inclusion criteria will be randomized and will report for their scheduled appointments as per standard practice. Once the patient arrives into the procedure room, the appropriate sealant technique will be prepared based on the assigned randomization arm. If the patient was randomized to the manufactured plug arm, the device will be made available at the start of the procedure. If the patient was randomized to the blood patch arm, then before the start of the procedure, phlebotomy will be performed, drawing 2-3 mL of the patient's blood into a labeled anticoagulant-free syringe which will be capped and left to clot in a cap-down position.

The specific anatomical site of the biopsy will be selected by the interventional radiologist. All standard protocol for lung biopsy will be followed routinely including NPO status, monitored sedation, and withholding of anticoagulation medications along with aspirin and clopidogrel bisulfate as per guidelines of MSKCC IR service. All biopsies will be performed using coaxial technique under CT guidance.

A limited CT scan of the lesion and adjacent lung parenchyma is acquired for biopsy planning. A biopsy path will be chosen to avoid pulmonary blebs, fissures, and pulmonary and superficial vessels, while the patient is positioned accordingly.

A biopsy path traversing at least 1.5 cm of aerated lung will be preferred so that an effective ABPI or BioSentry might be applied. Biopsies will be performed by any of the attending interventional radiologists or by an interventional radiology fellow under the direct supervision of an attending. A small sterile field is set. Local anesthesia will be used. An Angiotech 19-gauge introducer needle will be advanced into the corresponding lung with the needle tip at the near edge of the lesion. A 20-gauge automatic spring-loaded core biopsy gun (for example Temno, ACT) or a 20-22 Gauge FNA needle (for example Westcott) will be used to obtain core tissue and/or FNA samples. A cytotechnologist will be present on-site for all biopsies to assess adequacy of tissue samples as per standard of care.

Once the sample has been deemed adequate, and prior to removal of the guiding needle, the appropriate sealant technique will be delivered based on the patient's randomization arm.

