If the patient was assigned to the ABPI group, a blood patch will be administered using the clotted blood in the syringe obtained at the beginning of the procedure. The guiding needle will be retracted up to 1.5-2 cm from the pleural surface, and the blood will be injected steadily and gently as the needle is pulled back out of the pleura. Injection will stop when the operator feels the needle is in subcutaneous tissues.

If the patient is assigned to BioSentry group, using the manufacturer's deployment device (Figure 1) the introducer needle is positioned so that the tip is at least 1.5 cm deep to the visceral pleura. The coaxial introducer needle hub will be prehydrated with a drop of saline, the BioSentry plug housing will be mated and locked to the hub and the plug will be deployed.

If during the biopsy procedure, there was onset of a pneumothorax before deployment of autologous or manufactured plug, or there was more than one pleural puncture, or passage through a fissure, a bleb, non aerated lung, the sealant may be administered if still technically feasible, and the decision will be at the discretion of the operator. If a coaxial system was not used, the sealant cannot be administered. These cases will be included in the primary intent-to-treat analysis, but excluded in a secondary per-protocol analysis:

- More than 1 needle pass through visceral pleura
- Passage of needle through pleural fissure, bleb, or bulla
- Passage of needle through consolidated or non-aerated lung
- Co-axial biopsy system not used
- Development of pneumothorax before deployment of BioSentry or ABPI
- Use of introducer needle larger than 19 gauge
- Needle length more than 15 cm

We expect that less than 5 percent of all biopsies may end up being excluded during the procedure from intraprocedural complications precluding the use of a tract sealant.

After the procedure, all patients will be transferred to the recovery unit where at least two chest radiographs will be obtained immediately and 2 hours after the procedure according to standard of care. Additional radiographs may be obtained if indicated according to standard of care.

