14.0 BIOSTATISTICS

This is a randomized trial comparing autologous blood patch injection with BioSentry on the rate of pneumothorax after percutaneous lung biopsy. The primary endpoint is the rate of pneumothorax within 2 hours following biopsy. Pneumothorax is observed on post procedure CT scan or on follow-up chest radiographs while the patient is in the recovery room, according to standard of care.

This study will have a non-inferiority design to evaluate whether ABPI is associated with less than a 10% increase in pneumothorax rate compared to BioSentry. We will test the null hypothesis that ABPI is inferior, with a 10% or more increase in pneumothorax rate compared to BioSentry. The non-inferiority margin of 10% is considered clinically acceptable. Allowing for 1 interim assessment, the study will require 276 patients in each arm (552 patients total) to have 90% power to test this hypothesis. This sample size estimate assumes the pneumothorax rate with tract plug is approximately 20% based on a randomized study by Zaetta et al. An interim assessment will be performed after approximately half the patients (roughly 276 patients) have been enrolled onto the study. Using the Lan-DeMets spending function, the trial will terminate early for non-inferiority if with half the patients, a one-sided nominal Z-score of -2.538 ($p\text{-value} \leq 0.0056$) is observed. This nominal z-score will be recalculated based on the available exact information fraction at the time of the Data Safety Monitoring Board review. If the trial continues, the final assessment will use a Z-score of -1.662 with an associated $p\text{-value}$ of 0.0482. This preserves a 5% overall probability (1-sided type I error) of falsely concluding that ABPI is non-inferior to tract plug when it is truly worse. In 2012 IR service performed 1128 lung biopsies. IR service currently performs around 100 lung biopsies each month. With an anticipated eligibility rate of 50%, this study will take up to 24 months.

All randomized patients who undergo a biopsy will be analyzed for the primary outcome on a modified intent-to-treat basis according to the randomized treatment assignment regardless of the actual intervention received. The difference between pneumothorax rates for ABPI and BioSentry will be estimated and assessed using a Z-test. The same analysis method will be used to perform a secondary analysis on only patients who have a sealant placed after their biopsy.

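### Sections 4.3 and 14.0 give two unreconciled populations for the one per-protocol analysis of 2-hour pneumothorax listed in Section 2.1

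*Combined protocol and SAP*

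**What the plan says.** - **Section 2.1** lists, as a secondary objective, a comparison of pneumothorax "within 2 hours following image guided biopsy in a per-protocol analysis". It does not define the population.
- **Section 4.3** lists seven situations: more than one pleural pass; passage through a fissure, bleb or bulla; passage through consolidated or non-aerated lung; no coaxial system; pneumothorax before deployment; an introducer larger than 19 gauge; and a needle longer than 15 cm. It then says "These cases will be included in the primary intent-to-treat analysis, but excluded in a secondary per-protocol analysis". For several of these, "the sealant may be administered if still technically feasible, and the decision will be at the discretion of the operator"; only the non-coaxial case rules a sealant out. Section 7.0 repeats the discretion.
- **Section 14.0** sets the primary analysis as modified intent-to-treat in all randomised patients who undergo a biopsy. It adds one further analysis of that endpoint: "The same analysis method will be used to perform a secondary analysis on only patients who have a sealant placed after their biopsy". It does not call this per-protocol, does not mention the seven situations, and does not say whether the sealant must be the assigned one.
- **Section 20.4 (Physician Data Form)** allows no sealant as an entry, with a reason. Its item on intraprocedural pneumothorax does not say whether the event came before or after deployment.

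**The concern.** The per-protocol objective has no single answer: two analysts who each follow the plan could report different results from the same data, and the choice could be made after the data are seen. In a non-inferiority trial the per-protocol result is the usual check that the intent-to-treat comparison has not blurred a real difference, so its population should be fixed in advance.

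The group that matters most falls under this item of the Section 4.3 list: "Development of pneumothorax before deployment of BioSentry or ABPI". Such an event cannot be a failure of a sealant not yet deployed. Section 4.3 removes it; Section 14.0 keeps it whenever the operator goes on to seal. That operator knows the arm, because on arrival in the procedure room "the appropriate sealant technique will be prepared based on the assigned randomization arm".

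**Working it through.** **Plan's own figures.** For equal rates of 20%, a 10-point margin, one-sided 5% and 90% power, the fixed design needs (1.645 + 1.282)² × 2 × 0.20 × 0.80 / 0.10² ≈ 274.1, so 275 per arm. With the interim look, 276 per arm gives 90.0%. The boundaries −2.538 and −1.662 also reproduce. None of these figures is in dispute.

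**The two sets side by side**

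| Patient | Section 4.3 | Section 14.0 |
|---|---|---|
| None of the seven, sealed | in | in |
| One of the seven, sealed at discretion | out | in |
| One of the seven, not sealed | out | out |
| None of the seven, not sealed | in | out |

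Neither set contains the other, and neither section refers to the other.

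**Illustration, Section 14.0 set.** From the plan: 2-hour rate 20% (taken as true in both arms) and the 10-point margin. Assumed: *f*, the share of patients with a pneumothorax before deployment that is counted at 2 hours, and *s*, the share of those who are sealed. All other patients are taken as sealed.

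Rate in the set = (*f·s* + 0.20 − *f*) / (*f·s* + 1 − *f*)

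Example with *f* = 5%: *s* = 0.2 gives 0.16/0.96 = 16.67%; *s* = 0.8 gives 0.19/0.99 = 19.19%; the difference is 2.53 points.

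| Sealed, one arm v other | *f* = 1% | *f* = 2% | *f* = 5% |
|---|---|---|---|
| equal | 0 | 0 | 0 |
| 40% v 60% | 0.16 | 0.33 | 0.84 |
| 20% v 80% | 0.48 | 0.98 | 2.53 |
| 0% v 100% | 0.81 | 1.63 | 4.21 |

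Entries are spurious differences in percentage points. The arm that seals more looks worse. If only half of these pneumothoraces are counted at 2 hours, the middle two rows fall to 0.06–0.32 and 0.18–0.95.

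Equal sealing does not make the set neutral if the arms truly differ. If 5% of the set in each arm are sealed pre-deployment events, a true 10-point difference in the remainder shows as 0.10 × 0.95 = 9.5 points.

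**Illustration, Section 4.3 set.** Suppose a share *m* of one arm has a true sealant failure recorded as a pre-deployment event. The shift is (0.20 − *f*)/(1 − *f*) − (0.20 − *f* − *m*)/(1 − *f* − *m*). For *m* = 0.5%, 1% and 2% this is 0.41, 0.82 and 1.67 points at *f* = 1%, and 0.45, 0.90 and 1.81 at *f* = 5%.

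**Power of a smaller set.** With 5% excluded, 276 × 0.95 ≈ 262 per arm. At a 20% rate, final-look power is 0.885, against 0.900 at 276. If everyone excluded was a counted pneumothorax, the remaining rate is 0.15/0.95 = 15.8% and power is 0.931.

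**The case against.** **The texts can be read together.** Section 14.0 never uses the per-protocol label. Both conditions might be meant to apply, or Section 14.0 might describe an additional as-treated analysis. Section 4.3 follows its list by expecting under 5% of biopsies to be "excluded during the procedure from intraprocedural complications precluding the use of a tract sealant", which suggests the authors saw exclusion and non-sealing as largely the same group. This stands so far as it shows the rules can be reconciled. But no section states a joint rule, and if Section 14.0 is a separate analysis, the one promised in Section 2.1 is missing from the statistics section. Either reading needs an edit.

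**The effect may be nil.** This also stands. Nothing in the documents suggests that sealing would differ by arm, and the milder cases are 0.2–0.3 points against a margin of 10. The under-5% figure does not settle the matter, though: it covers complications that preclude a sealant, not patients with a listed situation who are sealed anyway, and those are where the two rules part.

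**Stronger readings that the documents do not support.**
- A reader might infer that the Section 4.3 set is free of operator influence. It avoids only the sealing decision. The number of punctures, the needle path, coaxial use and the recorded timing of a pneumothorax also arise after randomisation with the arm known.
- A reader might infer from the data form that needle-path hemorrhage leads to patients going unsealed. The form lists it among factors affecting outcome; no section says it leads to no sealant. That a patient with none of the seven is left unsealed is a logical possibility of unstated frequency.

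**Conclusion.** The point holds as a conflict between two stated rules for one secondary analysis. It rests on the text and not on the illustrations. The size cannot be computed from the documents, which give neither the frequency of the seven situations nor the share sealed. Under assumed shares of 1–5% the spurious difference in the Section 14.0 set runs from 0 with equal sealing to 4.2 points at 0% v 100%; the direction is unknown. Mis-recorded timing could move the Section 4.3 set by about 0.4 to 1.8 points under similar assumptions.

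A reader might infer that the trial's main conclusion is at risk. It is not: the primary modified intent-to-treat rule keeps these patients whatever sealant they received, and the sample size and stopping boundaries are unaffected.

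**What to change.** In Section 14.0, replace the sealed-patients rule with one per-protocol definition and use it in Section 4.3 as well: randomised and biopsied patients who received the assigned sealant and had none of the seven situations listed in Section 4.3. If the set with any sealant placed is also wanted, name it as a separate sensitivity analysis. Tabulate by arm the patients who leave each set and why, including those unsealed or given the other sealant. On the data form, record whether an intraprocedural pneumothorax was seen before or after deployment. Settle this before outcome data are reviewed.

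The cost is a sentence in Section 14.0, a matching edit in Section 4.3 and one form item. The secondary set becomes slightly smaller. The 262 per arm used above is only an illustration; requiring the assigned sealant could remove more patients. Membership still depends on post-randomisation events, so the result should be read as supportive of the modified intent-to-treat analysis. The primary rule, sample size, boundaries and clinical management do not change.

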20.4 PHYSICIAN DATA FORM

Effect of Autologous Blood Patch Injection versus BioSentry hydrogel Tract Plug in the reduction of pneumothorax risk following lung biopsy procedures

1- Patient Demographics

MRN		Procedure date		/	/	
Last Name		Male	Female	DOB	/	/

2- Candidate for study Yes No

If no, please explain why or list/circle exclusion criteria #:

3- Consent obtained Yes No

4- Randomization # _____

5- Procedure parameters

Exclusion criteria

1. Passage through non-aerated lung or tissue OR Target lesion located LESS than 1.5 cm away from visceral pleura
2. Needle path transgressing pleural fissure or bleb
3. Coaxial technique not needed
4. Needle size 17 gauge
5. Prior ipsilateral lung interventions: biopsy, chest tube, surgery, radiation or pleurodesis

Target size (largest transverse diameter on reference image) _____ cm

Target depth (Needle path distance from pleura to outer edge of target) _____ cm

Lobe (please circle) RUL RML RLL LUL LLL

Position (please circle) Prone Other:

Type of biopsy (please circle) FNA Core Both

Number of biopsy samples FNA: Core:

6- Factors affecting outcome: Did you encounter (please circle)

More than 1 pleural puncture? Yes No

Passage through a fissure? Yes No

Complete passage through non aerated lung? Yes No

Passage through a bleb/bulla? Yes No

Usage of BARE needle WITHOUT coaxial system? Yes No

Intraprocedural pneumothorax? Yes No

Significant needle path hemorrhage within 2 cm of pleura? Yes No

7- Sealant technique used (please circle) Blood patch BioSentry None
 (Please note reason below)

8- Outcomes

Pneumothorax on CXR (please circle) Yes No

Pneumothorax - Second reader (please circle) Yes No

Chest tube placement (please circle) Yes No

Delayed complications (please circle) Yes No If Yes: _____

Notes:

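### The per-protocol set is defined in two different ways, and neither requires that the patient received the sealant assigned, so crossovers can stay in the trial's only check on dilution

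*Combined protocol and SAP*

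**What the plan says.** Section 2.1 makes a per-protocol analysis of the 2-hour pneumothorax rate a secondary objective. Two places then describe its population.

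- **Section 4.3** lists seven deviations: more than one pleural pass; a fissure, bleb or bulla crossed; non-aerated lung crossed; no coaxial system; pneumothorax before the sealant; an introducer larger than 19 gauge; a needle longer than 15 cm. It says of them: "These cases will be included in the primary intent-to-treat analysis, but excluded in a secondary per-protocol analysis". Receipt of the other arm's sealant is not on the list.
- **Section 14.0** says: "The same analysis method will be used to perform a secondary analysis on only patients who have a sealant placed after their biopsy". Any sealant qualifies; it need not be the assigned one.

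The primary analysis in section 14.0 is by arm as randomized: "according to the randomized treatment assignment regardless of the actual intervention received". The sentence after that names the Z-test on the difference in rates, and the secondary analysis follows. Section 14.0 does not restate which arm a crossover counts in for the secondary.

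The data needed are collected. The physician data form (section 20.4) records: "7- Sealant technique used (please circle) Blood patch BioSentry None".

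**The concern.** In a non-inferiority trial, patients who receive the other arm's treatment make the arms more alike. If ABPI is truly worse, this shrinks the observed gap and favours a non-inferiority finding. Analysis by assignment accepts that dilution, and a per-protocol analysis is the usual check on it. Here it is the only one planned, since no as-treated analysis is stated.

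As written, the check removes procedural deviations (section 4.3) or unsealed patients (section 14.0), but under neither rule does it remove a patient who got the wrong product. Agreement between primary and secondary would then say little about crossover. That matters because section 3.0 gives the purpose as justifying exclusive use of ABPI.

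The two definitions also select different patients. Section 4.3 allows the sealant to be placed after several of the listed deviations, and such a patient is out under 4.3 but in under 14.0. A patient left unsealed with no listed deviation is in under 4.3 but out under 14.0.

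**Working it through.** **Inputs from section 14.0**

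- Margin: 10 points ("The non-inferiority margin of 10% is considered clinically acceptable").
- Error rate: "This preserves a 5% overall probability (1-sided type I error) of falsely concluding that ABPI is non-inferior to tract plug".
- Size: "the study will require 276 patients in each arm (552 patients total) to have 90% power to test this hypothesis".
- BioSentry rate: "This sample size estimate assumes the pneumothorax rate with tract plug is approximately 20" per cent. I take the same rate for ABPI under the alternative.
- Boundaries: Z = -2.538 at half the patients and Z = -1.662 at the end.

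**Reproducing the plan's figures**

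- Fixed design, unpooled variance: n = (1.645 + 1.282)² × (0.20×0.80 + 0.20×0.80) / 0.10² ≈ 274.1, so 275 per arm.
- O'Brien-Fleming-type Lan-DeMets spending at information fraction 0.5: 2 − 2Φ(1.960/√0.5) = 0.00557, so the interim boundary is 2.538. The final boundary that brings the total to 5% is 1.662 (p = 0.0482).
- With both boundaries and 276 per arm, overall one-sided error is 5.0% and power is 90.0%. The plan's figures reproduce.

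**Effect of keeping crossovers under the assigned arm**

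True rates are set at the margin: ABPI 30%, BioSentry 20%. A share c is assumed to cross over at random.

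- One-way (ABPI to BioSentry): ABPI arm = 0.30(1−c) + 0.20c; gap = 0.10(1−c).
- Two-way: in addition, BioSentry arm = 0.20(1−c) + 0.30c; gap = 0.10(1−2c).
- Standard error = √{[pA(1−pA) + pB(1−pB)]/276}; drift = (0.10 − gap)/standard error at the final look, multiplied by √0.5 at the interim. The false non-inferiority rate is the bivariate normal probability of crossing either boundary.

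Example, one-way at c = 5%: pA = 0.295 and pB = 0.20. Standard error = √[(0.208 + 0.160)/276] = 0.0365. Drift = 0.005/0.0365 = 0.137. The final look alone gives 1 − Φ(1.662 − 0.137) ≈ 6.4%; both looks together give 6.6%.

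| Assumed c | One-way gap (points) | One-way error | Two-way gap (points) | Two-way error |
|---|---|---|---|---|
| 0 | 10.0 | 5.0% | 10.0 | 5.0% |
| 2% | 9.8 | 5.6% | 9.6 | 6.2% |
| 5% | 9.5 | 6.6% | 9.0 | 8.5% |
| 10% | 9.0 | 8.5% | 8.0 | 13.5% |

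**How much of the primary's dilution the secondary shares**

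Take two-way crossover of 5%. Suppose also that 5% of each arm gets no sealant, with a 31% pneumothorax rate (the untreated control figure in section 3.0).

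- Primary: gap = 0.95 × 9.0 = 8.55 points; error 10.5%.
- Section 14.0 any-sealant set, crossovers as assigned, 262 per arm (276 × 0.95): gap = 9.0 points; error 8.4%.

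The any-sealant set carries the crossover part of the drift but not the no-sealant part.

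**If the assigned sealant is required**

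If crossover is unrelated to risk, the gap returns to 10 points and the error to 5.0%. Removing only a share c from each arm, power is 89.4% at 2% (270 per arm), 88.6% at 5% (262) and 87.1% at 10% (248).

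The two-look boundaries are used for the secondary only as illustration, since no interim look at it is described.

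**The case against.** **Classification in the secondary is not explicit.** A reader might infer that crossovers stay under their assigned arm in every planned analysis. The text says this only for the primary. The phrase about the same method could mean the Z-test alone, and the per-protocol label in section 2.1 ordinarily implies that the assigned treatment was received. This stands: counting crossovers as assigned is the natural reading, not a stated rule. What remains is that neither definition takes them out.

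**The secondary does not share all of the primary's drift.** A reader might infer that it does. The section 14.0 set drops unsealed patients, so it shares only the crossover part.

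**Crossover may be rare.** Sections 4.3, 9.0 and 15.3 have the sealant prepared according to the randomized arm, and 4.3 has it delivered by arm. The operator's discretion in 4.3 is whether to seal, not which product to use. The varying preferences in section 9.0 describe routine practice. ABPI needs blood drawn beforehand and left to clot, so switching to ABPI is the harder direction and two-way crossover the less plausible case. Some events that might prompt a departure are already exclusions under 4.3. All this stands, and it is why the one-way figures lead; at 2% the effect is small.

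**The primary decision is not changed.** The inflation at 276 per arm belongs to the primary, which stays as it is, and section 14.0 gives the secondary no decision role. A reader might infer that the fix lowers the trial's false-positive risk. It does not; it only makes the supporting check able to show the problem.

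**Dropping crossovers can itself bias.** If operators switch by patient risk or technical difficulty, exclusion loses the protection of randomization, in either direction. This also stands.

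**Conclusion.** The point holds in a limited form. The per-protocol population has two conflicting definitions, neither requires the assigned sealant, and the arm in which a crossover counts in the secondary analysis is not stated. On the natural reading, the per-protocol check shares the crossover part of the dilution it should help to expose.

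The size depends on a crossover rate that the documents do not give. The range runs from negligible if crossover is close to nil to a false non-inferiority rate of 8.5% at 10% one-way crossover, or 13.5% at 10% two-way. These figures assume random crossover, true rates of 30% and 20%, and the 276-per-arm two-look design. The plan's sample size and boundaries are sound as stated. The correction is worth making because it costs almost nothing and uses a field already on the form.

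**What to change.** Replace the two descriptions in sections 4.3 and 14.0 with one per-protocol definition: patients who received the sealant they were assigned (data form item 7) and had none of the deviations listed in 4.3, analysed by assigned arm. Adding a clause to each section separately would leave the two definitions in conflict.

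Beside the primary result, report by arm the number of crossovers and the number with no sealant, with reasons. The form's prompt for a reason sits next to the *None* option, so make clear that it covers crossovers too. Leave the modified intention-to-treat primary unchanged.

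The cost is a short protocol amendment and one line of analysis code. The secondary set becomes slightly smaller, and selection bias is possible if switching follows patient risk or technical difficulty. State in section 14.0 that this analysis is read beside the primary and does not replace it.
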